**3. Abstract:**

Previous research demonstrates that non-Hispanic blacks (NHB) with osteoarthritis (OA) experience more frequent and severe clinical pain, greater disability and show a quantitative sensory testing (QST) profile suggesting impaired pain inhibition and enhanced generalized pain facilitation compared to their non-Hispanic white (NHW) counterparts. In addition, previous findings demonstrated higher pain catastrophizing (a tendency to negatively evaluate one's ability to cope with pain and to respond to anticipated or actual pain in a heightened negative cognitive and emotional manner) among NHBs compared to NHWs. While multiple factors inevitably contribute, race group differences in cognitive and affective processes (e.g. catastrophizing), represent potentially important determinants of greater clinical pain among NHBs, perhaps by altering central pain processing. Despite its pervasive negative effects, no neuroimaging study to date has experimentally manipulated pain catastrophizing and measured cerebral activity during experimentally-induced pain to determine the neural mechanisms whereby catastrophizing impacts pain responses. Moreover, the extent to which the influence of pain catastrophizing on these central pathways contributes to ethnic group differences in the experience of pain remains unexplored. To address this, the proposed study will characterize the impact of an anti-catastrophizing cognitive-behavioral intervention on pain-related neural processes and pain among NHBs and NHWs with knee OA. NHB and NHW participants with symptomatic knee OA will be randomly assigned to a brief pain catastrophizing reduction cognitive-behavioral intervention or a control group that will receive pain education. Testing will occur over three days. Participants will complete neuroimaging, including assessment of pain-evoked cerebral responses and experimental pain testing (i.e., QST) prior to and after the intervention session. Standardized quantitative sensory testing approaches will be used to assess experimental pain sensitivity, as well as their State Pain Catastrophizing Scale (S-PCS). We hypothesize that baseline levels of catastrophizing will be higher among NHB subjects and will predict increased pain sensitivity and greater pain-related brain responses among NHB participants. Moreover, we anticipate that the anti-catastrophizing reduction intervention will produce greater reductions in reported pain and in pain-related brain activity among NHB versus NHW participants. Findings from this proposed study will provide novel information regarding the neural mechanisms whereby pain catastrophizing modulates pain and the extent to which these neural processes contribute to ethnic group differences in pain responses among NHBs and NHWs with knee OA. This project will yield important preliminary data for a future grant application seeking support for a larger scale clinical intervention study targeting pain catastrophizing to reduce disparities in pain among older adults.

**4. Background:**

Clinical osteoarthritis (OA) is the most commonly diagnosed disease with prevalence rates of approximately 27 million US adults and rates are projected to increase as the population age [26; 31], resulting in an annual economic cost of \$128 billion [8]. The knee is the most commonly affected joint and accounts for the largest proportion of OA burden [54]. Data from a large

representative study revealed that non-Hispanic blacks (NHB) have higher odds of being diagnosed with radiographic (1.7 times) and clinical (1.5 times) knee OA than non-Hispanic whites (NHW) [14]. Furthermore, NHBs with knee OA have higher prevalence rates of radiographic and symptomatic knee OA and they experience substantially higher levels of knee OA-related chronic pain, functional limitations, and disability compared to their NHW counterparts [2; 22; 52]. In addition, NHBs with knee OA show deficits in pain modulation during experimental pain testing, such that they evince enhanced pain facilitation and impaired pain inhibition compared to NHWs [11]. This quantitative sensory testing profile likely contributes to greater experimental and clinical pain sensitivity and may be a phenotype of pain risk in NHBs. Together, these findings suggest that ethnic group differences in central pain processing represent a potentially important determinant of greater clinical pain among NHBs. While numerous factors likely contribute to ethnic differences in OA-related pain and other adverse outcomes [3; 19], interventions targeting psychosocial factors have been shown to be a promising avenue to reduce pain and reverse aberrant central pain processing in patients with chronic pain [27; 41], but less emphasis has been devoted to addressing ethnic differences in knee OA using interventions aimed at addressing psychosocial factors [1].

A robust psychosocial predictor of enhanced pain and pain-related outcomes is pain catastrophizing. Pain catastrophizing is a tendency to negatively appraise pain-related experiences, thereby feeling overwhelmed and having lower perceived ability to cope with and control pain, thus, resulting in an amplified pain experience and adverse pain-related outcomes (e.g., disability) [30; 43; 44]. Considerable evidence identifies pain catastrophizing as a consistent psychosocial variable that predicts poor pain and pain-related outcomes [34; 50] across multiple chronic pain conditions [18; 23; 33; 38; 45-47; 51], including in patients with knee OA [6; 28; 29]. Numerous studies have documented higher pain catastrophizing in healthy pain-free NHBs compared to NHWs during experimental pain tasks [35]. Similarly, investigations of race difference in pain catastrophizing in patients with knee OA and other chronic pain conditions, suggest NHBs report higher pain catastrophizing during both experimental and clinical pain, compared to NHWs [10; 16; 21; 39]. While the importance of intervening on pain catastrophizing has been established, research is needed to better understand its neural correlates in order to improve treatment efficacy [42].

Neuroimaging studies have associated pain catastrophizing with increased cerebral responses to pain in several pain-related brain regions (e.g., medial frontal cortex, anterior cingulate cortex [ACC], dorsolateral prefrontal cortex [dIPFC], insula, and primary somatosensory cortex [SI]) [9; 15; 18; 40], and with increased resting state connectivity between SI and insula [27]. A recent systematic review of brain changes associated with pain catastrophizing reveal there is some evidence for alterations in gray matter morphology and resting state functional connectivity in patients with chronic pain following reduction of pain catastrophizing [32]. Indeed, compelling evidence demonstrates that successful reduction of pain catastrophizing following cognitive behavioral therapy was significantly correlated with gray matter increase in several pain related brain regions (e.g., dIPFC, S1, ACC) [41]. Furthermore, reduction of pain catastrophizing with cognitive behavioral therapy resulted in the decoupling of resting state connectivity between SI and anterior/medial insula, brain regions not typically connected in a resting state [27]. However, Malfliet et al. [32] notes that these studies were observational, which limits conclusions about the causal effects of the treatment of pain catastrophizing and its influence on brain alterations. Therefore, no neuroimaging study to date has experimentally manipulated pain catastrophizing and measured cerebral activity during experimentally-induced pain to determine the neural mechanisms whereby catastrophizing impacts pain responses. Moreover, the extent to which the influence of pain catastrophizing on these central pathways contributes to ethnic group differences in the experience of pain remains unexplored.

The objective of the proposed research is to experimentally manipulate pain catastrophizing in order to investigate the neural mechanisms by which pain catastrophizing influences the

experience of pain among NHBs and NHWs with chronic pain associated with knee OA. Therefore, participants will be randomized to either a 30-minute, single-session catastrophizing reduction manipulation or a 30-minute, single-session pain education control group [48; 49].

## 5. Hypotheses and Specific Aims:

**Specific Aim 1:** To characterize the impact of an anti-catastrophizing manipulation on pain-related neural processes and pain among NHBs and NHWs with knee OA.

Hypothesis 1a. We hypothesize that the manipulation will produce greater reductions in experimental pain and clinical pain among NHBs than NHWs.

Hypothesis 1b. We hypothesize that the manipulation will produce greater reductions in pain-related brain responses among NHBs than NHWs.

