## 6. Research Plan:

The proposed study will enroll 5 NHB and 5 NHW catastrophizing participants with symptomatic knee OA. The study will over-enroll 3 additional participants due to attrition over the three-day study period. Up to 180 additional participants may undergo screening procedures and will count toward screen failures. Potential participants will undergo a standardized telephone or in-person screening which will include the pain catastrophizing questionnaire, as well as screening questions that inquire about conditions that are listed under our inclusion and exclusion criteria to confirm initial eligibility. Participants will be informed that if they do participate in this study, we will keep the information the participant provide in addition to information provided to these questions as part of this research study. If the participant does not meet inclusion criteria or decides not to participate in the study, the participant will be informed that no additional information would be collected, but any information up to that point would be maintained. Thirty potential participants will be screened to determine initial eligibility. Patients will be excluded if they have concurrent medical or arthritic conditions that could confound symptomatic knee OA related outcome measures or coexisting disease that could preclude successful completion of the protocol including: systemic rheumatic disease/condition, including rheumatoid arthritis, systemic lupus erythematosus, gout, and fibromyalgia; a history of clinically significant surgery to the index knee (e.g. open reconstruction, knee replacement or major surgery on one or both knees); uncontrolled hypertension ( $> 150/95$ ); loss of peripheral sensation in areas of the body that will be tested with QST; certain neurological diseases that could interfere with protocol completion such as s Parkinson's disease, multiple sclerosis, stroke with loss of sensory or motor function, or uncontrolled seizures; cardiovascular or peripheral arterial disease; serious psychiatric disorder requiring hospitalization within the past 12 months; diminished cognitive function that would interfere with completion of study procedures. Daily opioid use will also be an exclusion, as well as a Pain Catastrophizing Score of less than 10. Hospitalization within the preceding year for psychiatric illness, serious psychiatric disorder requiring hospitalization within the past 12 months or characterized by active suicidal ideation or diminished cognitive function that would interfere with completion of study procedures. Pregnancy will also be an exclusion. Also, contraindications to MRI scanning (e.g. presence of metal implants, claustrophobia) will be exclusion criteria. Any criteria for MRI Exclusion, such as the presence of non-removable metallic, magnetic material or devices such as pacemakers, aneurism clips, or claustrophobia, which could pose a risk for injury in the MRI scanner. The study will include questionnaires to assess pain, clinical symptoms, and pain catastrophizing. All questionnaires provided during this research study's timeline are shown in Table 2. Quantitative Sensory Testing (QST) will be performed at the Pain Clinical Research Unit (PainCRU), a fully equipped sensory testing lab within the UF Pain Research and Intervention Center of Excellence (PRICE) directed by [name] (mentor).

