**Neuroimaging Protocol.** A high-resolution, 3D structural scan will be conducted using a T1-weighted MP-RAGE sequence for use in pre-processing all functional data which will be conducted between stimulus-evoked scans (Table 1). Two **resting state scans** will be acquired using BOLD-fMRI and pCASL in order to examine functional connectivity. Participants will be asked to close their eyes during resting state scans, but to maintain alertness during the scans. Any difficulty staying awake was assessed immediately following the resting-state scan. **Stimulus-Evoked fMRI and pCASL:**

These procedure will be conducted to assess changes in regional brain activity to painful mechanical stimuli applied to the most painful knee of OA patients. Specifically, a monofilament that was individually calibrated to produce a moderate pain intensity rating of  $\leq 50$  out of 100 will be applied once per second for a total of five twenty-four second blocks to the index knee, followed by an equivalent time period of blunt stimulation (randomized order) with thirty-six second blocks

Table 2. Questionnaires administered by visit day

Day 1	Day 2	Day 3
Health History	Positive and Negative Affect Scale (PANAS)	Positive and Negative Affect Scale (PANAS)
Pain History	Western Ontario and McMaster Universities Osteoarthritis Index (WOMAC)	Treatment Expectation Questionnaire
REALM-R	Graded Chronic Pain Scale (GCPS)	Manipulation Check Questionnaire
Physical Exam Form	State Pain Catastrophizing Scale (S-PCS)	Coping Strategies Questionnaire-Revised (CSQ-R)
MRI Screening Form		State Pain Catastrophizing Scale (S-PCS)
Pain Catastrophizing Scale (PCS)		

Note: All questionnaires will be administered after written documentation of consent. S-PCS questionnaires will be administered after each pain testing task.

Table 1. MRI Sequences

Run	Paradigm	Min
-	Positioning	9.5
1	Resting fMRI BOLD Scan	8
2	Resting pCASL Scan	5
3	Mechanical Pain fMRI BOLD Scan	10
4	Anatomical Scan: T1 Weighted Image (3D)	4.5
5	Mechanical Pain pCASL Scan	10
6	Resting DWI HARDI Scan	7.5
7	FLAIR 3D (OPTIONAL Time Permitting)	5.5
		Total Time 60

of rest between each mechanical stimuli. One overall verbal pain rating (on the 0-100 scale) will be obtained following all stimuli. Data acquisition of all scans will occur in two 50.5-minutes imaging session, with 9.5 minutes for set up, resulting in a total 60-minute session.

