**Randomization and General Procedures.** Individuals will be randomized to one of two groups (stratified by sex): 1) a 30-minute, single-session cognitive-behavioral intervention designed to reduce pain catastrophizing or 2) a control condition that receives pain education. Testing will occur on two days (Figure 1). On Day 1, participants will attend a laboratory session whereby informed consent will be reviewed; health, pain, and demographic history will be obtained and physical examination will be performed to identify the most symptomatic knee. Female participants of childbearing potential will complete a one-time pregnancy test at the beginning of the session on day one. Trait pain catastrophizing will be assessed prior to pain testing. Day 1 session is expected to last up to 1.5 hours. On Day 2, participants will undergo neuroimaging acquisition followed by assessment of State Pain Catastrophizing Scale (S-PCS) in response to the pain-evoked cerebral responses (see **neuroimaging protocol** above). Then, participants will complete QST assessment of responses to pressure (i.e., pressure pain threshold), and punctate mechanical stimuli (i.e., temporal summation of mechanical pain) in a laboratory session lasting 30-60 minutes. State Pain Catastrophizing Scale (S-PCS) will be assessed immediately after each pain induction procedure. There will be a 30-minute rest period between the neuroimaging and QST session. Day 2 session is expected to last 2.5 to 3 hours. On Day 3, each participant will receive either the cognitive-behavioral intervention or the pain education (control condition), followed by post-tests that will be identical to the pre-tests given on Day 2, except that participants in the pain catastrophizing reduction group will be told to use the coping strategies they learned. Once all testing is over, participants will be debriefed and provided with an honorarium. Day 3 testing session is expected to last 3 to 3.5 hours. Audio recording will be conducted at the end of the study in order to obtain feedback on what intervention techniques participants used and whether they noticed any difference during Day 3 testing. We will audio record responses to the following questions: 1) during this last testing, please tell us what you were able to do; 2) describe how you applied your techniques; 3) did you notice any difference in your reactions to the stimulations; and 4) what did you notice? Further, participants will be asked to rate on a scale from 0-10 how well they were able to use the strategies and how effective they felt the strategies were. These recording will be reviewed by the study team to assess the quality of our treatment visits. These recording will not be released and will only be accessible by study investigators. At the end of the study, the recordings will be transcribed and the audio recordings will be destroyed. State Pain Catastrophizing Scale (S-PCS) will be used as a manipulation check to verify that catastrophizing was effectively. **Pain Catastrophizing Reduction Group:** The cognitive-behavioral intervention will comprise three components: 1) general education about pain (e.g., pain pathways) and a rationale for the intervention (e.g., gate control theory); 2) impact of positive and negative pain-related thoughts on neural process of pain; and 3) a guided imaginal pain exposure exercise. We and others have successfully applied these and similar approaches to reducing pain catastrophizing [12; 13; 48; 49] (see manual for details). **Pain Education Group:** This group will receive general information about the neurobiology of pain and knee OA. At no time will they be taught about pain modulation or the interface of thoughts, feelings, and pain [48; 49].

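### Table 2 lists both clinical-pain scales only before the intervention, so as listed the clinical-pain part of Hypothesis 1a has no post-manipulation outcome, and the text on post-tests conflicts with the table or leaves the matter open

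*Combined protocol and SAP*

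**What the plan says.** Section 5, Hypothesis 1a, states: "We hypothesize that the manipulation will produce greater reductions in experimental pain and clinical pain among NHBs than NHWs". It names experimental and clinical pain as two separate things.

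Section 6, Data Analysis, tests the manipulation with separate ANCOVAs on neural and pain outcomes. Baseline values are covariates and post-manipulation values are dependent variables.

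Section 6, under Clinical Pain, describes WOMAC and then GCPS. GCPS looks back over six months. No recall period is given for WOMAC.

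Section 6 also says: "All questionnaires provided during this research study's timeline are shown in Table 2". In that table WOMAC and GCPS stand in the Day 2 column and nowhere else.

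Under Randomization and General Procedures, the intervention or pain education is given on Day 3, "followed by post-tests that will be identical to the pre-tests given on Day 2". The one stated exception is that the reduction group is told to use its coping strategies. The visit ends the study: "Once all testing is over, participants will be debriefed and provided with an honorarium".

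**The concern.** An ANCOVA on a post-manipulation outcome cannot be fitted if the outcome is never collected. Read literally, Table 2 gives clinical pain a baseline covariate and no dependent variable. A Day 3 score that was not taken cannot be recovered afterwards, so the gap has to be closed before participants reach Day 3.

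What is at stake is limited but real. The study is small: "The proposed study will enroll 5 NHB and 5 NHW catastrophizing participants with symptomatic knee OA". It is meant to supply preliminary data for a larger intervention study. Even so, clinical pain is half of the only listed hypothesis about pain.

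**Working it through.** No sample-size, power or alpha figure is involved. The check sets the sections side by side.

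**1. What the hypothesis and model require.** A reduction in clinical pain (section 5), analysed with a post-manipulation dependent variable (Data Analysis). At least one clinical-pain score is needed after the Day 3 session.

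**2. What Table 2 lists, by questionnaire.**

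| Questionnaire | Day 2 (before) | Day 3 (intervention day) |
|---|---|---|
| PANAS | yes | yes |
| S-PCS | yes | yes |
| WOMAC | yes | no |
| GCPS | yes | no |
| Treatment Expectation | no | yes |
| Manipulation Check | no | yes |
| CSQ-R | no | yes |

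Day 2 has 4 items and Day 3 has 5. Two are common, two are on Day 2 only and three are on Day 3 only. Both Day 2-only items are the clinical-pain scales. Nothing listed on Day 3 is a clinical-pain scale by its name. Because PANAS and S-PCS are written out under both days, the absence of WOMAC and GCPS from Day 3 does not look like shorthand.

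**3. Count under Table 2.** Planned participants: 5 + 5 = 10; with over-enrolment, 10 + 3 = 13. Clinical-pain scales with a post-manipulation value: 0 of 2. Participants with such a value: 0 of 10, or 0 of 13.

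**4. Does the procedures text fill the gap?** The sentence on identical post-tests does not define pre-tests. The Day 2 account in the same paragraph begins "On Day 2, participants will undergo neuroimaging acquisition followed by assessment of State Pain Catastrophizing Scale (S-PCS" and goes on to QST, without naming WOMAC or GCPS. The Abstract likewise places neuroimaging and QST before and after the session. These favour the narrow reading, in which only imaging, QST and S-PCS are repeated. On the wide reading, all Day 2 questionnaires would recur, and the sentence would contradict Table 2.

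**5. Do the visit lengths decide between the readings?** Day 3 is 180 to 210 minutes. Taking off the 30-minute session leaves 150 to 180 minutes, exactly the Day 2 length. That fits either reading.

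**6. Could another measure serve?** The 0-100 rating in the scanner is given after the evoked stimuli, so it is experimental pain. If GCPS were repeated on Day 3, its six-month window would make it poorly suited to change on the day of a 30-minute session. WOMAC could serve only if its recall period, at present unstated, allowed it.

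**The case against.** The strongest reply is that the procedures text already covers the matter. Post-tests are to match the Day 2 pre-tests with one stated exception, and leaving out two questionnaires is not that exception. This stands as a reason not to read the plan as certainly omitting the measure. It does not rescue the schedule, because it then conflicts with a table that the protocol calls complete.

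Table 2 may also be less complete than claimed. The catastrophizing questionnaire is part of screening, yet the table shows it on Day 1 only. All analyses are to adjust for discrimination, yet no discrimination measure is listed by name, although one could sit within a history form. This weakens the inference from the table's silence and is a further reason to reconcile the text.

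A reader might also infer that clinical pain has no test by ethnic group at all, since the interaction model is described in terms of brain responses. The documents do not support that. Data Analysis names clinical pain among the ethnic-group comparisons of the primary aim, and the word again, introducing the interaction models, may carry them over to the pain measures. The wording is imprecise; a missing test is not shown.

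Nor does the Abstract confine the prediction to experimental pain. It predicts reductions in reported pain and in brain activity, and reported pain does not exclude clinical pain.

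Finally, Day 2 WOMAC and GCPS have a use without any repeat, in a baseline comparison of the ethnic groups. That is true, but a baseline comparison cannot test a reduction.

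**Conclusion.** The point holds with moderate confidence and should be fixed. As Table 2 is written, 0 of 10 participants (0 of 13 with over-enrolment) would have a post-manipulation WOMAC or GCPS score, and the clinical-pain part of Hypothesis 1a could not be tested. The experimental-pain part, Hypothesis 1b, imaging, QST, S-PCS and a baseline comparison of clinical pain are untouched. No bias or loss of power is claimed.

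It would go too far to say that the study will not measure clinical pain after the session. The plan is contradictory or ambiguous on this, and the conclusion is conditional on staff following the table.

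It also rests on the column layout of Table 2 as read from PDF. That layout is plausible, since the intervention-specific forms fall under Day 3. Figure 1 and the study Timeline to which the Research Plan refers could not be checked; either might settle the question.

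**What to change.** Reconcile Hypothesis 1a, Table 2, the sentence on identical post-tests and the Data Analysis paragraph, and state which Day 2 assessments are repeated on Day 3. Then take one of two routes.

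(a) **Measure it.** List WOMAC in the Day 3 column, after the session, with a stated recall period suited to same-day change and the same period used on Day 2. Name it as the clinical-pain dependent variable, and make clear that the ANCOVA with the manipulation-by-ethnic-group term covers it. Do not rely on the six-month GCPS for same-day change. The cost is a few minutes on Day 3, for data that remain preliminary at this sample size.

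(b) **Narrow the claim.** Remove clinical pain from the reduction claim in Hypothesis 1a, and use WOMAC and GCPS as pre-intervention measures only. The cost is a change of wording and a narrower stated claim; no procedure changes.
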